1.0 INTRODUCTION/BACKGROUND

Brain metastases are the most common adult intracranial tumor, occurring in approximately 10% to 30% of adult cancer patients, and represent an important cause of morbidity and mortality in this population.¹ The risk of developing brain metastases differs with different primary tumor histologies, with lung cancer accounting for approximately one half of all brain metastases.² The prognosis of patients with brain metastases is poor. The median survival time of untreated patients is approximately 1 month.³ With treatment, the overall median survival time after diagnosis is approximately 4 months.⁴ The RTOG recursive partitioning analysis (RPA) describes three prognostic classes, defined by age, Karnofsky Performance Score (KPS), and disease status.⁵ The most widely used treatment for patients with multiple brain metastases is WBRT. The appropriate use of WBRT can provide rapid attenuation of many neurological symptoms, improve quality of life, extend median survival, and be especially beneficial in patients whose brain metastases are surgically inaccessible or when other medical considerations preclude surgery.^{6,7} The use of adjuvant WBRT after resection or stereotactic radiosurgery (SRS) has been proven to be effective in terms of improving local control of brain metastases, and thus, the likelihood of neurological death is decreased.⁸

The majority of patients who achieve local tumor control die from progression of extracranial disease, whereas the cause of death is most often due to CNS disease in patients with recurrent brain metastases.^{7,8} Currently, no consensus on the optimal radiation schedule for patients with brain metastases is established. Standard treatment regimens include dose fractionation schemes evaluated in the early RTOG studies and range from 20 Gy in 5 fractions to 40 Gy in 20 fractions. The exact regimen used is generally at the discretion of the treating physician and often depends upon issues such as the severity of CNS symptoms, the extent of systemic disease, and physician preference.

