This previous version of this study was a phase I dose escalation trial giving 25 Gy in 10 fractions to the whole brain with simultaneous infield boost (SIB) to a total of 45 Gy in 10 fractions to gross brain metastatic disease. Prior to this, patients were enrolled onto one of two cohorts with whole brain dose of 30 Gy in 10 fractions with SIB to total of 45 Gy in 10 fractions to gross brain metastatic disease or whole brain dose of 37.5 Gy in 15 fractions with SIB to total of 52.5 Gy in 15 fractions to gross brain metastatic disease. A total of 12 patients have been previously enrolled on this trial. No patients have experienced a dose limiting toxicity (grade 3 or above) at least possibly due to study therapy. Also, no patients experienced local brain failure/progression at a site of treated metastatic brain disease. Based on this, we no longer feel that dose escalation to the gross brain disease is warranted and would proceed with a single arm pilot study treating patients with 25 Gy in 10 fractions to the whole brain with simultaneous infield boost (SIB) to a total of 45 Gy in 10 fractions to gross brain metastatic disease.

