2.0 OBJECTIVES

2.1 Primary Objectives

- 2.1.1 To determine the feasibility of treating brain metastasis patients with whole brain radiation and simultaneous focal boost using an RA technique. (see Section 11.4)
- 2.1.2 To determine the locoregional control [at visible lesion(s) and new site(s)] in the brain of patients treated with a concomitant boost RA plan.

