11.3.4 Definition of CNS progression

CNS progression will be defined as a > 25% increase in volume for any tracked brain metastasis, or the appearance of any new brain metastasis on a follow-up MRI. For lesions smaller than 1 cm in maximum diameter, a maximum increase of 50% in volume will be necessary to score as progression. This caveat is included to account for potential variability in measurement, which will be most susceptible to proportionate errors at smaller sizes. For greater than 1 cm lesions, the definition will use a 25% rule for change.

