13.0 STATISTICAL CONSIDERATIONS

13.1 Study endpoints

13.1.1 Primary endpoints

- Feasibility – Measurement of the amount of time required for daily treatment
- Rates of toxicities
- Local brain control
- Regional brain control

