13.2 Sample size

This will be a single cohort pilot study. Safety of the chosen dose level has been shown based on the previous phase I dose escalation iteration of this study.

18 patients will be enrolled consecutively into this single arm pilot study.

If a patient is not able to complete follow up to the toxicity assessment point of 4 months due to a toxicity judged not to be at least possibly related to therapy, then that patient will be replaced by the next patient enrolled.

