13.3 Statistical Analysis

Descriptive statistics will be performed on the clinical and treatment factors on subjects on this study. Categorical data will be presented on frequency tables while continuous data will be presented as mean, standard deviation, median and range. Local control, regional brain control, progression-free survival and overall survival will be assessed using the Kaplan-Meier method with censoring as appropriate. Univariate and multivariate analysis will be performed with these endpoints to determine patient factors that may influence outcome. These curves will also be compared to previously published results as historical controls. The results of the neurocognitive and quality of life surveys/tests will be plotted for each patient to assess for a general trend over time. The trend over time can also be analyzed by linear regression analysis. Each point in time can be compared with historical controls using a student's t-test to determine whether there is a significant difference in the survey/test scores in patients on our study versus historical results.

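### Section 13.3 names no interval for local control, and the default Kaplan-Meier interval is degenerate if no local failure is seen

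*Combined protocol and SAP*

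**What the plan says.** Section 13.1.1 lists "Local brain control" among the primary endpoints, with regional control as a separate item. Section 2.1 words the objective more broadly: "To determine the locoregional control [at visible lesion(s) and new site(s)] in the brain".

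The analysis in section 13.3 is one sentence: "Local control, regional brain control, progression-free survival and overall survival will be assessed using the Kaplan-Meier method with censoring as appropriate". The same section goes on to compare these curves with published results as historical controls. It gives no interval, confidence level, variance formula or landmark time.

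On size, section 13.2 says that "18 patients will be enrolled consecutively into this single arm pilot study". It states no precision target and no expected local failure rate.

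Section 1.0 reports the earlier experience: "A total of 12 patients have been previously enrolled on this trial", and "no patients experienced local brain failure/progression at a site of treated metastatic brain disease". Those patients came from more than one dose cohort, and their length of follow-up is not given. The protocol cites this result as part of its reason for stopping dose escalation.

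**The concern.** With 18 patients, one arm and no formal test, the interval is the main measure of what the trial has learned about local control. The protocol's own record makes zero failures a realistic result, and that is the one result for which standard Kaplan-Meier output carries no usable uncertainty. A flat curve at 100% looks the same whether 18 or 6 patients are still being followed at the time of interest.

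Early deaths sharpen the problem. Section 1.0 says: "With treatment, the overall median survival time after diagnosis is approximately 4 months". That figure is for treated patients in general, and entry here requires KPS of at least 70, so survival may be longer. Even so, the number at risk at 6 months could be far below 18. A flat curve placed beside published curves, without a valid interval, invites a firmer conclusion than the data allow. Treating death as a competing event does not remove the difficulty, because the usual variance of a cumulative incidence is also zero when no event is seen.

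**Working it through.** The plan states no interval or precision figure, so there is nothing of its own to reproduce. The check asks what the default method gives at zero failures, how often zero failures would occur, and what a valid interval would show.

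**Inputs from the protocol:** n = 18 (13.2); Kaplan-Meier (13.3); 0 local failures in 12 (1.0); median survival about 4 months (1.0), used as the low end of a range.

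**Assumptions, not in the documents:** 95% level; 6-month landmark; true 6-month local failure q of 5%, 10% or 15%; median survival M of 4 to 9 months; independent exponential times to failure and death, with deaths censored. A zero-failure interval counts as missing the truth.

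**1. The interval at zero failures.** The Greenwood variance is S² × Σ d/[r(r − d)], where d is the number of failures and r the number at risk at each failure time. With no failures the sum is empty, so the variance is 0 and S = 1. The plain interval is 100% to 100%. The log-log interval divides by ln(S) = 0 and is undefined. The number at risk does not enter.

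**2. The interval at one failure.** For 1/18 without censoring, S = 17/18 = 94.4%:
- plain: 83.9% to 100% (capped)
- log-log: 66.6% to 99.2%
- Clopper-Pearson: 72.7% to 99.9%

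The plain lower limit is too high, but nothing collapses, and the log-log lower limit is below the exact one.

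**3. Chance of zero failures.** Let λ = −ln(1 − q)/6 and μ = ln 2/M. The chance that a patient has an observed local failure by 6 months is p = λ/(λ + μ) × [1 − exp(−6(λ + μ))], and P(0) = (1 − p)^18. For q = 5% and M = 4: λ = 0.00855, μ = 0.17329, p = 0.0470 × 0.6641 = 0.0312, and P(0) = 0.9688^18 = 56.5%. Without deaths, P(0) = (1 − q)^18.

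**4. Coverage.** By simulation of the same model, plain coverage given at least one failure is 99.0% to 99.8% across these settings, and log-log coverage is 91% to 96%. Overall plain coverage is therefore close to 1 − P(0). For q = 5% and M = 4: (1 − 0.565) × 0.997 = 43%.

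| True 6-month failure | P(0): M = 4 | P(0): M = 9 | P(0): no deaths | Plain coverage: M = 4 | M = 9 | no deaths |
|---|---|---|---|---|---|---|
| 5% | 57% | 48% | 40% | 43% | 52% | 60% |
| 10% | 31% | 22% | 15% | 68% | 77% | 84% |
| 15% | 17% | 10% | 5% | 82% | 89% | 94% |

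With deaths, overall log-log coverage is 3 to 4 points lower in each setting.

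**5. What 0/12 says about q.** The exact two-sided 95% upper limit is 1 − 0.025^(1/12) = 26.5%. At that rate, zero failures in 18 would be seen in 0.735^18 = 0.4% of trials without deaths.

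**6. A valid lower limit at zero failures.** With m patients at risk at the landmark, the limit is 0.025^(1/m):
- m = 18: 81.5%
- m = 8: 63%
- m = 6: 54%

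The last two are conservative, because they give no credit to patients followed for part of the period. An m near 6 is plausible: with median survival of 4 months, 18 × 0.5^(6/4) = 6.4 patients are expected to be alive at 6 months.

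**The case against.** The strongest reply is that section 13.3 prescribes no interval at all, so the plan contains no faulty one. That is correct. The gap is an omission, and the degenerate interval is what default output would supply.

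Second, the evidence that failures will be rare is thin. The 0/12 result pools dose cohorts, has no stated follow-up, and is compatible with failure rates up to 26.5%. Section 11.3.4 also sets a low bar: "CNS progression will be defined as a > 25% increase in volume for any tracked brain metastasis". A 25% volume increase is about 8% in diameter (1.25^(1/3) = 1.077), although lesions under 1 cm need 50%. A reader might infer that zero or near-zero failures are what the trial will show. The documents support only that zero is a realistic possibility.

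Third, a reader might infer that Kaplan-Meier intervals fail with few events generally, or that coverage here is 40-50%. Neither holds. The collapse is confined to exactly zero failures, and coverage near 40-50% belongs to particular assumed failure and survival rates.

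Fourth, the zero-failure record concerns treated lesions only. Section 1.0 says nothing similar about new brain sites, so the point does not carry over to regional control or to the locoregional objective as a whole.

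Finally, this is a pilot with no decision rule tied to the interval, and the method could be chosen at reporting. That limits the weight of the point. It does not remove it, because an interval method chosen after a 100% result is seen is less credible than one fixed beforehand.

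**Conclusion.** The concern holds in a limited form. For a primary endpoint that will be set beside published curves, the plan names Kaplan-Meier and no interval. If no local failure occurs, as in the earlier 12 patients, the default interval is 100% to 100% or undefined, whatever the number at risk.

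Its size depends on rates that the documents do not give. Across 5% to 15% true 6-month failure and median survival of 4 to 9 months, zero failures would be seen in about 10% to 57% of trials, and nominal 95% plain coverage would range from about 89% down to 43%. Almost all the shortfall is the chance of exactly zero failures. These figures also rest on exponential times and on death being independent of local failure. The algebra at zero failures rests on none of these assumptions.

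**What to change.** Add to section 13.3:
- Report local control at fixed landmarks, for example 6 and 12 months, each with the number at risk.
- Give a 95% interval that is valid at zero events: the beta-product interval for the Kaplan-Meier estimate, or Clopper-Pearson limits when nobody is censored before the landmark.
- Show that interval in any comparison with published curves.

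The 12-month figure may carry little information. With median survival of 4 months, 18 × 0.5^(12/4) = 2.25 patients would be expected to be alive then, which is why the number at risk must be printed.

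The cost is a few sentences and standard software, with no change to design, conduct or data collection. The only downside is a wider, somewhat conservative interval: without censoring, Clopper-Pearson coverage was 96.6% to 99.5% for failure rates from 2% to 26.5%, and beta-product coverage was 98% to 100% in simulations with deaths.

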
Varian Medical Systems has notified and received clearance from the Food and Drug Administration (FDA) to use RapidArc in patient care. This technology is not considered an experimental device. The standard of care for patients with 1 – 4 brain metastases is currently WBRT with or without SRS boost. Patients with more than 4 brain metastases are typically eligible for WBRT only. With an integrated boost method, we believe that we can deliver increased dose to the gross disease, in a more convenient and time efficient manner, include patients who would not otherwise be SRS candidates, and spare more normal brain tissue, which may translate into improved local control and median survival. We believe that the risk:benefit ratio is favorable for patients who would be enrolled on this study due for several reasons: the current very poor prognosis of the condition, the use of an existing FDA approved technology, and the integration of a proven treatment into a more efficient regimen.

Given the limitations of the SRS boost technique, the purpose of our investigation is to evaluate an alternative strategy for giving WBRT with highly focal boost to gross visible lesions in patients with brain metastasis. In this study, we plan to assess the tolerability of using volumetric modulated arc therapy (RapidArc) on patients with brain metastasis to simultaneously treat the entire brain with a concomitant focal boost to grossly identified lesions on MRI scan to try to improve local control and reduce neurocognitive toxicities.

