3.0 PATIENT SELECTION

3.1 Inclusion Criteria

- 3.1.1 Pathologic proven diagnosis of solid tumor malignancy.
- 3.1.2 Age ≥ 18 .
- 3.1.3 KPS ≥ 70 .
- 3.1.4 Mini Mental Status Exam (MMSE) ≥ 18 prior to study entry.
- 3.1.5 RPA class I (KPS ≥ 70 , primary cancer controlled, age < 65 , metastases in brain only) or class II (lack of one or more of class I criteria) (see **Appendix A** for definitions).
- 3.1.6 One to ten brain metastatic lesions.

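### The pooled local-control curve for patients with 1 to 10 lesions is compared with published results without matching on lesion number, so case mix and choice of benchmark can pass for a treatment effect

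*Combined protocol and SAP*

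**What the plan says.** - **Who is enrolled.** Section 3.1 admits "One to ten brain metastatic lesions". Sections 5.0 and 13.2 put all 18 patients in a single cohort. Section 1.0 says that the technique is meant to "include patients who would not otherwise be SRS candidates".
- **Standard of care.** Section 1.0 gives two: "The standard of care for patients with 1 – 4 brain metastases is currently WBRT with or without SRS boost", and "Patients with more than 4 brain metastases are typically eligible for WBRT only".
- **Endpoint.** Section 13.1.1 lists "Local brain control" as primary and lists regional control separately. Neither has its own event definition or unit of analysis.
- **Failure rule.** The only rule is in section 11.3.4: "CNS progression will be defined as a > 25% increase in volume for any tracked brain metastasis", or any new metastasis, with a 50% threshold for lesions under 1 cm.
- **Analysis.** Section 13.3 applies Kaplan-Meier to local control, regional control, progression-free survival and overall survival, with no strata, and then states: "These curves will also be compared to previously published results as historical controls". It names no source, matching rule or test for that comparison.
- **Tension within section 13.** The heading of 13.1.2 attaches historical controls to the secondary endpoints only. The wording of 13.3 extends them to local control.

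**The concern.** Two separate problems arise when one curve for 1–10 lesions is set beside published results.

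**Comparator.** By the protocol's own account, the treatment these patients would otherwise receive depends on lesion number. A pooled curve has no single matching benchmark. The apparent result depends on whether the chosen series received WBRT plus SRS or WBRT alone, and on how many trial patients have more than 4 lesions.

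**Lesion count.** If a patient fails as soon as any treated lesion grows, a patient with ten lesions has ten chances to fail and a patient with one lesion has one. Patient-level control then falls with lesion count even though no lesion is treated less effectively. The randomised boost trial cited in section 1.0 covered one to three metastases, according to its title in the reference list. A series of that kind would differ from this cohort in lesion count alone.

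At stake is how a primary endpoint is read: the same data could look better or worse than standard care for reasons unrelated to the boost.

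**Working it through.** There is no planned figure to reproduce. Section 13.2 gives 18 patients without a historical rate, target effect, alpha or power, and 18 is not disputed here. The documents also give no lesion-count distribution, per-lesion failure rate or published control rate, so everything below rests on stated assumptions.

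**Step 1. Patient-level control by lesion count.** Let *p* be the per-lesion failure probability, the same in every patient, and *k* the number of lesions.

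- Independent lesions: control = (1 − *p*)^*k*.
- Within-patient correlation ρ (beta-binomial): control = Γ(*b*+*k*)Γ(*a*+*b*) / [Γ(*b*)Γ(*a*+*b*+*k*)], with *a* = *p*(1/ρ − 1) and *b* = (1 − *p*)(1/ρ − 1).

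| ρ | *p* | 1 lesion | 3 | 4 | 10 |
|---|---|---|---|---|---|
| 0 | 0.05 | 95.0% | 85.7% | 81.5% | 59.9% |
| 0 | 0.10 | 90.0% | 72.9% | 65.6% | 34.9% |
| 0 | 0.20 | 80.0% | 51.2% | 41.0% | 10.7% |
| 0.5 | 0.05 | 95.0% | 91.1% | 89.9% | 86.2% |
| 0.5 | 0.10 | 90.0% | 82.6% | 80.6% | 74.0% |
| 0.5 | 0.20 | 80.0% | 67.2% | 63.8% | 53.8% |

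**Step 2. A whole cohort against a 1–3 lesion series.** Assume that the series has equal shares of 1, 2 and 3 lesions and is scored per patient by the same rule. Assume that half the trial patients have 1–4 lesions and half have 5–10, evenly spread within each group. Per-lesion failure is identical throughout, so the true treatment difference is zero.

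Worked case, *p* = 0.10, ρ = 0:

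- Series: (0.900 + 0.810 + 0.729)/3 = 0.813.
- Trial, 1–4 lesions: (0.900 + 0.810 + 0.729 + 0.656)/4 = 0.774.
- Trial, 5–10 lesions: (0.590 + 0.531 + 0.478 + 0.430 + 0.387 + 0.349)/6 = 0.461.
- Trial overall: 0.5 × 0.774 + 0.5 × 0.461 = 0.617.
- Difference: 0.617 − 0.813 = −0.196, about −20 points.

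Spurious difference in points (trial minus series), all cases:

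| | *p* = 0.05 | *p* = 0.10 | *p* = 0.20 |
|---|---|---|---|
| ρ = 0 | −12 | −20 | −25 |
| ρ = 0.2 | −7 | −12 | −17 |
| ρ = 0.5 | −3 | −6 | −9 |

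Over the same grid, the range is about −2 to −16 points if a quarter of patients have 5–10 lesions, and −4 to −35 if three quarters do.

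**Step 3. Choice of benchmark.** Assume control of 85% with WBRT plus SRS and 70% with WBRT alone. If patients with 1–4 lesions are matched to the first and the others to the second, the benchmark is 0.85(1 − *s*) + 0.70*s*, where *s* is the share with more than 4 lesions. It is 85% at *s* = 0, 77.5% at *s* = 0.5 and 70% at *s* = 1. Using WBRT alone for everyone at *s* = 0.5 would flatter the trial by 77.5 − 70 = 7.5 points. This bias runs opposite to that in Step 2.

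**Step 4. Precision.** Clopper-Pearson 95% intervals: 14 of 18 controlled gives 52–94%; 7 of 9, in an assumed even split, gives 40–97%.

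**The case against.** **The unit of analysis is not documented.** Section 11.3.4 defines CNS progression, not local failure, and section 11.3.3 evaluates each treated lesion. A reader might infer that the plan scores local control per patient on any lesion; the documents do not say so. They lean that way: section 1.0 describes the 12 earlier patients in terms of whether any had failed at a treated site, and section 12.2 takes a patient off study at local progression. This stands as a qualification. A per-lesion analysis would shrink the count effect but leave the comparator mismatch.

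**The size can be overstated.** Setting 3 lesions against 10 under full independence gives gaps of 85.7 − 59.9 = 26 points and 72.9 − 34.9 = 38 points. That compares two extreme patients, not two cohorts. At ρ = 0.5 the same gaps are 91.1 − 86.2 = 5 and 82.6 − 74.0 = 9. If per-lesion control were 99%, the independent gap would be 97.0 − 90.4 = 7. The absence of local failures in the 12 earlier patients suggests low failure, but weakly, since their follow-up is not stated. Much of the 3 to 25 point range also lies within the sampling error of 18 patients.

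**The trial does not set out to replace SRS.** A reader might conclude that it fails to answer whether the boost substitutes for SRS. Section 2.0 contains no such objective; it asks for feasibility and for locoregional control to be determined. The point therefore concerns only the comparison that section 13.3 adds.

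**Lesion number does not settle the comparator.** For 1–4 lesions, section 1.0 makes the SRS boost optional, so WBRT alone is also a stated standard. It adds that SRS is generally contraindicated for lesions above 3–4 cm. Not every patient with 1–4 lesions could have had it.

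**Covariates are planned.** Section 13.3 foresees univariate and multivariate analysis of patient factors. The factors are unnamed, so lesion count is neither included nor excluded. Such an analysis works within the trial and does not adjust a comparison with outside curves.

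**Conclusion.** The concern holds in a limited form. The plan pools 1–10 lesions, states two standards of care by lesion number, and compares the resulting local-control curve with unnamed published results without matching on lesion number. That part needs no assumption.

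The size does. If local failure is a patient-level event on any treated lesion, case mix alone produces a deficit of about 3 to 25 points against a 1–3 lesion series, given 5–20% failure per lesion, correlation of 0–0.5 and half the patients with 5–10 lesions. The count effect can only lower the trial's figure against a series with fewer lesions. The net bias has no fixed direction, because a WBRT-alone benchmark for patients with 1–4 lesions can favour the trial.

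This limits the interpretation of an exploratory comparison on a primary endpoint. It does not touch the feasibility criterion in section 11.4 or the cohort's own description of local control.

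**What to change.** In section 13.3:

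1. **Define the event and unit.** State that the patient-level local-control event is growth of a treated lesion, kept separate from new lesions. Beside it, report per-lesion local control with standard errors clustered by patient. State how a patient's remaining lesions are censored, since section 12.2 ends participation at local progression and that censoring may be informative. Compare each estimate only with published results that use the same unit.
2. **Stratify by the protocol's own cut.** Report local control descriptively for 1–4 and for 5–10 lesions, and make any historical comparison within these strata. Set 1–4 lesions against WBRT plus SRS and, labelled as a separate question, against WBRT alone. Set 5–10 lesions against WBRT alone. Name each source and its lesion range, because a 1–3 lesion series still does not fully match a 1–4 lesion stratum.
3. **Draw no conclusion from the pooled historical comparison of local control.**

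Sections 11.3.2 and 11.3.3 already collect volumes lesion by lesion, so no new measurement is needed. The changes are wording plus an explicit censoring rule. The price is precision: in an even split, 7 of 9 controlled spans 40–97%, so the stratified comparison can only be descriptive.

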4.0 PRE-TREATMENT EVALUATION

- 4.1 MRI scan with and without contrast (at least 5mm resolution on T1 post-contrast imaging).
- 4.2 History and physical including a detailed neurologic exam.
- 4.3 Steroid and anti-convulsant doses must be documented.
- 4.4 Baseline MMSE.
- 4.5 Baseline neurocognitive function using the HVLT-R (memory).
- 4.6 Baseline neurocognitive function using MOS (self-report).
- 4.7 Baseline QOL assessment using FACT-Br.
- 4.8 Documentation of extent of systemic disease.
- 4.9 Pregnancy test in women of child bearing potential when there is clinical suspicion of pregnancy

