12.2 Criteria for patient to be considered off study

- 12.1.1 Local CNS disease progression.
- 12.1.2 Patient death.
- 12.1.3 Patient request to come off study.
- 12.1.4 Patient is discharged to hospice

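### Visit-by-visit t-tests of raw cognitive and quality-of-life scores, and a regression of unstated unit, can misstate change when patients leave in relation to their scores

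*Combined protocol and SAP*

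**What the plan says.** Section 13.3 (Statistical Analysis) holds the whole analysis plan for these endpoints.

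- Results "will be plotted for each patient to assess for a general trend over time". This is the only firm commitment.
- "The trend over time can also be analyzed by linear regression analysis". The unit of analysis and the handling of repeated scores from one patient are not stated.
- "Each point in time can be compared with historical controls" by Student's t-test, to determine "whether there is a significant difference in the survey/test scores in patients on our study versus historical results". The quantity tested is the score itself; change from baseline is not mentioned.

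Elsewhere:

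- Section 4.0 collects baseline MMSE, HVLT-R, MOS and FACT-Br.
- Sections 11.1.5 and 11.2.2 schedule testing at baseline and at 1, 3, 6, 12, 18 and 24 months, each with a window of 6 weeks either way.
- Section 12.2 takes patients off study for "Local CNS disease progression", death, own request, or when "Patient is discharged to hospice".
- HVLT-R gives recall, delayed recall and recognition (11.1.2), and FACT-Br gives five scales and a total (11.2.1). Section 13.3 does not say which score is analysed.
- The only missing-value text for these instruments is the item-level MOS scoring in 11.1.4. Nothing covers missed visits or loss.

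**The concern.** A raw mean at month 12 and a raw mean at baseline come from different sets of patients. Their difference mixes change within patients with change in who is left. The same mixing enters a regression that pools all scores across patients. If leavers score lower than stayers, decline is understated; if they score higher, it is overstated; if leaving is unrelated to score, there is no bias. The plan collects the baseline that would separate the two components but does not use it in the t-tests.

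What is at stake is the reading of a stated objective. Section 1.0 gives possible reduction of neurocognitive toxicity as part of the case for the lower whole-brain dose, and Section 2.2.3 lists long-term neurocognitive effects. A significant difference from history, or a flat trend, could reflect survivorship alone.

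**Working it through.** **Nothing to reproduce.** The 18 patients in Section 13.2 come without SD, effect size, alpha, power or loss rate.

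**Step 1. The mechanism, exactly.** Suppose 9 patients are constant at 40 and 9 constant at 60, so the true slope is 0 and the true mean 50. The low scorers leave after month 3. Taking one patient per group (the factor 9 cancels), there are 10 scores: both groups at 0, 1 and 3, and the high group at 6, 12, 18 and 24.

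- Mean time = (2×4 + 60)/10 = 6.8; mean score = (3×40 + 7×60)/10 = 54.
- Sxy = (40×4 + 60×64) − 10×6.8×54 = 4000 − 3672 = 328.
- Sxx = (2×10 + 1080) − 10×6.8² = 1100 − 462.4 = 637.6.
- Pooled slope = 328/637.6 = **+0.51 per month**, and visit means after month 3 are 60.

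If the high scorers leave instead, the slope is −0.51 and the later means are 40. Each patient's own slope and change from baseline are 0 in both cases.

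**Step 2. How many remain.** Section 1.0 gives a median survival of about 4 months for treated patients overall. Section 3.1.5 admits only RPA class I–II, so survival may be longer; medians m of 4 to 12 months are assumed. Expected alive = 18 × 2^(−t/m).

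| Median (months) | 4 | 6 | 9 | 12 |
|---|---|---|---|---|
| Alive at 12 months | 2.25 | 4.5 | 7.1 | 9.0 |
| Alive at 24 months | 0.3 | 1.1 | 2.8 | 4.5 |
| Chance of fewer than 3 alive at 24 months (binomial) | >99% | 90% | 44% | 14% |

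Only death is counted. Progression and hospice would add to the loss if testing stops there, although Section 1.0 reports that "no patients experienced local brain failure/progression at a site of treated metastatic brain disease" among 12 earlier patients.

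**Step 3. Loss related to score level.** Assumed, on a generic scale: between-patient SD 4, within-patient SD 2.5, slope −0.15 per month, and hazard = (ln 2/m) × exp(−g × baseline z). There were 2,000 simulated trials per scenario. The true decline is 0.15×6 = 0.9 at 6 months and 0.15×12 = 1.8 at 12.

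| Median (months) | 4 | 6 | 9 | 12 |
|---|---|---|---|---|
| Raw mean, size of bias at 6 months, g = ±0.25 | 1.0 | 0.7 | 0.4 | 0.4 |
| Same, g = ±0.5 | 1.8 | 1.4 | 0.9 | 0.7 |
| Raw mean, size of bias at 12 months, g = ±0.25 | 1.9 | 1.4 | 0.8 | 0.6 |
| Same, g = ±0.5 | 3.1 | 2.3 | 1.6 | 1.3 |
| Pooled slope, lower scorers leave sooner, g = 0.5 | +0.07 | +0.02 | −0.03 | −0.06 |
| Pooled slope, higher scorers leave sooner, g = −0.5 | −0.38 | −0.32 | −0.27 | −0.25 |

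With unrelated loss the pooled slope is −0.15 to −0.16. Pooled 95% CI coverage is 92–94% at g = 0, 82–91% at ±0.25 and 63–77% at ±0.5. The within-patient slope is −0.15 in all 20 scenarios. Mean change from baseline in the same patients is off by no more than 0.06 points, but **only because loss here depends on baseline level**.

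A second simulation on another scale, with loss driven by the last score, shows the same pattern. Against a true slope of −0.25 and a true 12-month mean of 47.0, the pooled slope was 0.00 or −0.50 and the mean 51.1 or 43.0, according to who left. The within-patient slope was −0.25 both times.

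**Step 4. Loss related to a patient's own rate of decline.** Patient slopes now vary (SD 0.15) and hazard depends on slope (log-hazard ±0.25 to ±0.5 per SD).

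- Within-patient and random-intercept slopes are −0.04 to −0.11 if steeper decliners leave sooner, and −0.19 to −0.26 if the reverse, with coverage 62–84%. Pooled coverage is 72–86%, so the within-patient slope has no advantage here.
- Change from baseline at 12 months is biased by up to about 1.5 points against a true −1.8, as much as the raw mean.
- Adding a random slope gave roughly 89–94% coverage with less bias (medians 4 and 9, log-hazard ±0.5). This is approximate, because up to about 10% of those fits failed.

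**Step 5. Choice of model.** With varying slopes and loss unrelated to anything, a random-intercept-only interval covers about 79–87%, against 92–95% with a random slope. The random slope is therefore needed even without informative loss.

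**The case against.** *The regression is per patient.* The sentence on regression follows the one on individual plots, and its trend most naturally refers back to them. A reader might infer that the plan prescribes a pooled fit ignoring clustering; the text does not say that. On the per-patient reading the slope is nearly unbiased when loss depends on score level. This stands, and reduces the regression half to a request for clarity. It does not touch the t-tests.

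*The comparison is with history, which also loses patients.* This stands too. The historical series is unnamed and may carry its own survivor selection, so part of the bias could cancel. A reader might infer that attrition will make this treatment look better than history. Progression and hospice exits make loss of worse-functioning patients plausible, but the documents do not establish which patients leave, or how the historical patients were selected.

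*Survivor means are correct for survivors.* True: the bias above is against the full enrolled cohort, a target that is undefined after death. But the difference between two raw visit means is then not the change in any one group of patients.

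*The wording is permissive and this is a pilot.* This limits the weight. It also leaves model, score and visits to be chosen after the data are seen.

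*Mixed models do not cure informative loss.* Correct, as Step 4 shows.

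**Conclusion.** The concern holds, and its weight rests on the raw-score t-tests. If loss is related to score level, the 12-month raw mean is off by 0.6 to 3.1 points against a true decline of 1.8 under the assumptions of Step 3, enough to hide the decline or more than double it. The regression needs its unit stated; the pooled-slope figures apply only if a pooled fit is what is done.

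Two further inferences are not supported: that change from baseline or a within-patient slope removes the problem altogether (Step 4), and that the bias has a known sign against historical controls.

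Every magnitude rests on assumed SDs, slopes, hazards and survival, none of them given in the documents. The direction and the existence of score-related loss are likewise open. No decision rule depends on these secondary endpoints, so the change is recommended rather than essential.

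**What to change.** In Section 13.3, for one named score per instrument (for example HVLT-R delayed recall, MMSE total, MOS 0–100 score, FACT-Br total):

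1. Replace the visit-wise t-tests and the linear regression with a repeated-measures model using all scores including baseline, with a random patient intercept and random slope. If it does not converge, use a random intercept with a small-sample cluster-robust standard error, or the mean of per-patient slopes.
2. Use actual time since radiotherapy. With 6-week windows (42/30.4 = 1.4 months) the month-1 visit can fall as late as month 2.4 and the month-3 visit as early as month 1.6, so nominal times overlap.
3. Report change from baseline with 95% CI, and show historical values descriptively.
4. Keep the individual plots, marking where and why each line ends. By visit, report the number assessed and the reason for each missing score (death, progression, hospice, other).
5. State that results describe patients while alive and on study, and that the model slope and change from baseline both remain biased if loss depends on a patient's own rate of decline.

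Cost: SAP wording, slightly more analysis, a reason code for missing scores, wider intervals and fewer significance claims. The historical comparison in Section 13.1.2 becomes descriptive for these two endpoints. No extra patients, visits or tests are needed. The result may be inconclusive: under the Step 3 assumptions the median 95% CI width for a random-intercept slope is about 0.38–0.47 points per month at median survival 4 months, 0.27–0.29 at 6, 0.20–0.21 at 9 and 0.18 at 12, against an assumed slope of −0.15. When patients decline at different rates, an honest interval will be wider still.
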